## V. Experimental Design and Methods:

- i) Provide concise description of experimental design and procedures to be used to accomplish study goals. Include precise descriptions of all tests and measurements, and their expected duration. Include optional testing and blinding/un-blinding procedures if applicable.

Research Design: A cluster randomized control trial will be used to test hypotheses. The NM Department of Health, Office of School and Adolescent Health provided a list of recommendations for schools with functioning SBHCs serving a large Hispanic student population. PI [name] successfully approached these schools about collaborating on the proposed research; they agreed (see Letters of Support). To limit the possibility of confounding effects, our collaborating high schools all share the following four characteristics: 1)

Enrollment/ethnicity: At least >700 enrolled students, with at least 40% Hispanic youth, 2) Environmental resources: at least one outdoor field, one gymnasium, and physical activity opportunities, 3) Food service resources: at least one cafeteria, competitive foods (foods brought into schools from outside vendors), and vending machines, and 4) a functioning SBHC. To further control for plausible alternative explanations of outcomes between groups, pretest differences will be compared between groups. The pretests will allow exploration of the possible size and direction of bias that may exist. Thus, the joint use of a pretest and a comparison group will allow examination of possible threats to validity (see Analyses). Assessments will be conducted at pretest (baseline) and annually for two more years (see Table 1). The assessment time waves will allow us to follow 9th grade students annually until their 11th grade year and 10th grade students until their 12th grade year.

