- Biomarkers include insulin, glucose, hemoglobin A1c, and lipids will be obtained in overweight/obese adolescents. Samples will be drawn after an ten hour overnight fast. Serum samples will be allowed to clot. All samples will be centrifuged on-site and transported in an ice chest with freezer packs to Tricore Laboratory for processing. Insulin resistance will be calculated using the homeostatic model assessment insulin resistance index [HOMA-IR = (Product of fasting insulin mU/L and fasting glucose mmol/L)/22.5] which has been shown to have reliable sensitivity and specificity in assessing insulin resistance. HOMA-IR increases with increasing insulin resistance.
- Dietary intake will be assessed by the Block Food Screener 2007 a validated food frequency questionnaire. This self-administered tool estimates an individual's usual intake over a period of 1 week. NutritionQuest (Berkeley, CA) will create the data base from the completed surveys for analysis.
- Physical activity will be assessed using the 3-Day Physical Activity Recall (3DPAR) and accelerometry. The 3DPAR has established instrument validity in adolescents based on concurrent observation with motion sensors. Objective assessments of physical activity will be obtained using the ActiGraph GT3X accelerometer (Shalimar, FL). The Actigraph has documented evidence of validity and inter-instrument reliability in children and adolescents. Consistent with previous studies, monitors will be attached to adjustable elastic belts and worn over the right hip during waking hours for 7 consecutive days. Accelerometer counts will be uploaded to a customized EXCEL macro written by [name] for determination of daily time spent in sedentary, light, moderate, vigorous, and moderate-to-vigorous physical activity. The age-specific count thresholds corresponding to these intensity levels will be derived from the MET prediction equation developed by Freedson and co-workers as published by Trost and colleagues and replicate the intensity categories used in population-representative objective monitoring studies (e.g., NHANES).
- We will assess change using readiness to change (casaa.unm.edu), sedentary behavior (Robinson, 1999), eating attitudes (Garner et al, 1982) and health related quality of life (Varni) by evaluating adolescents' status on these measures at assessment waves.

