- Treatment intervention (ACTION weight management program)- Participants with BMI  $\geq 85^{\text{th}}$  percentile (overweight/obese) at baseline will receive ACTION. Consistent with our approach in our NIH-funded pilot study, prior to their first session of ACTION, adolescents will be scheduled by the data collection team in the SBHC for fasting blood sampling to evaluate for impaired fasting glucose, insulin resistance and dyslipidemia. SBHC providers will review these results at the youth's first session of ACTION. Session 1 will begin with SBHC clinicians providing youth with an educational DVD on nutrition and physical activity. At this time, using MI-based approaches (e.g., emphasis on autonomy, support of self-efficacy) clinicians will review pertinent physical exam and laboratory findings with the adolescent, assess the adolescent's dietary and physical activity behavior, provide feedback about how their diet and activity compare to national recommendations, and elicit the participant's over-all response to this information. Next, providers will invite adolescents to discuss barriers to healthier eating and physical activity, as well as general and personal strategies that might be helpful in overcoming these obstacles. For youth who are not yet ready to engage in discussions about change, providers will openly and supportively explore ambivalence about dietary and physical activity change, with an eye to supporting autonomy and self-efficacy around behavior change. For youth who are interested in exploring a change behavior, as indicated by their change talk; providers will help youth identify and develop 1-2 strategies for enacting positive behavior changes for the upcoming weeks (in the interim between ACTION sessions). These plans might include topics such as how and when to conduct physical activity, and how and where to purchase healthy foods. Because of the broad-based consensus that long-term interventions are needed for long-term behavioral change across pediatric nutrition and physical activity, and based on our R21 outcomes, we propose doubling our prior ACTION intervention (8 sessions/1 year) to yield a total of 16 sessions (e.g., 8 sessions per academic year for two years). This type of approach is uniquely possible due to the close proximity that SBHCs have to participating youth.

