- Analysis of intervention effects: Analyses will be conducted in a multilevel framework to account for clustering within schools. Mixed effects linear regression (SAS Proc Mixed) will be utilized for continuous outcomes (e.g., minutes of moderate or vigorous physical activity, BMI z score) and the generalized estimating equation approach (SAS Proc Genmod) will be used for binary dependent variables (e.g., hypertriglyceridemia, prediabetes defined by glucose and hemoglobin A1c) to study intervention impact on physical, behavioral and biochemical outcomes after 2 years. The following main outcomes of interest will be assessed: (**Hypothesis 1a**) Incidence of overweight and obesity after 2 years among students who were not overweight or obese at baseline; (**Hypothesis 1b**) sweetened beverage consumption, fat intake, fruits and vegetable intake, whole grain consumption, and time in moderate and vigorous physical activity after 2 years; (**Hypothesis 2**) BMI z score and HOMA-IR (insulin resistance index score) after 2 years among those students who were overweight or obese at baseline. Additional outcomes that will be assessed in the cohort of students who are overweight or obese at baseline include waist circumference, percent body fat, blood pressure percentiles, and biochemistries (glucose, insulin, hemoglobin A1c, and lipids) after 2 years. Hypotheses will be tested at a 0.05 significance level, two sided. Descriptive statistics (e.g., means  $\pm$  SD, percentages) will be used to evaluate process data. Bivariate relationships of participants' BMI z score change to student attendance will be assessed in the intervention group and a multivariate analysis will be subsequently used to control for other demographic variables. An intention to treat analysis plan will be used. To that end, adolescents who complete a fraction of the sessions will still be accounted for in the analyses. Data imputation methods will be used for missing data. Additionally, we will assess number of sessions completed to determine how attendance is associated with outcomes. The study will assess BMI trends in NM using data from the Youth Risk Resiliency Survey (the NM version of the CDC's Youth Risk Behavior Survey) to evaluate secular trends. The study will use the school's demographic data on race/ethnicity, age, and free/reduced lunch meals to assess the representativeness of the recruited population. If the recruited population does not appear to be representative, we will use weighted data

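### The within-arm attendance analysis states demographic adjustment only, so motivation can pass for an attendance effect; baseline readiness and baseline BMI z should be named as covariates and the result labelled non-causal

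*Combined protocol and SAP*

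**What the plan says.** Two sentences in section V.iii, Analysis of intervention effects, concern attendance.

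- The first plans bivariate relationships: "BMI z score change to student attendance will be assessed in the intervention group". It then says that "a multivariate analysis will be subsequently used to control for other demographic variables".
- The second, after the intention-to-treat statement, says that "we will assess number of sessions completed to determine how attendance is associated with outcomes". It names no covariates. It may restate the first analysis or extend it to other outcomes.

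The demographics listed in section V.i, Data Collection Measurements, are age, sex, socioeconomic status, education and race/ethnicity. None of these measures motivation.

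The same section lists a motivation measure among the instruments: "We will assess change using readiness to change". It is taken by evaluating students' "status on these measures at assessment waves". Section V.i, Research Design, defines the waves: "Assessments will be conducted at pretest (baseline) and annually for two more years". Read together, these place a readiness score at baseline, before the ACTION sessions. That timing is an inference, because the Table 1 cited there is not in the text available.

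**The concern.** Attendance is not randomised. It is settled by the student after allocation, so any trait that makes a student both more likely to attend and more likely to lose weight produces an association even if the sessions do nothing. In a motivational-interviewing programme the obvious candidate is readiness to change. The protocol expects students to differ in it: the description of ACTION session 1 makes provision "For youth who are not yet ready to engage in discussions about change". Baseline BMI z is a second candidate, since it may influence both attendance and later change.

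What is at stake is how an attendance result is read. ACTION was extended from 8 to 16 sessions, and these are the only quantitative analyses in the plan that bear on the number of sessions. A significant slope could be taken as support for that number when it reflects who chose to come.

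**Working it through.** **No plan figure to reproduce.** The documents give no sample size, power or effect for the attendance analysis. The check is therefore a comparison of passages followed by an illustration.

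**Is readiness brought in by another rule?**

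- Pretest equivalence (V.iii) adds variables that differ between conditions, and adds them to the analysis of intervention effects. It does not govern a within-arm analysis.
- The baseline-covariate rule (V.iii) covers models with intervention coded 0/1 as a fixed effect, which is constant within one arm. Read generously, it could add baseline BMI z. It does not add readiness.

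**Inputs.**

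- Students: 480 per arm (VI.ii) at 120 per school (V.iii) gives 4 schools per arm. With 28 overweight or obese students per school after attrition (V.iii), 4 × 28 = 112. I take attendance to mean ACTION sessions, which only these students receive.
- Test: two-sided 0.05 (V.iii).
- Assumed, because the documents give none: r1 = correlation of motivation with attendance; r2 = correlation of motivation with BMI z reduction; rel = reliability of the readiness score. True session effect zero, motivation the only common cause, clustering ignored.

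**Formulas.**

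- Spurious attendance–BMI z change correlation: −r1 × r2.
- Unadjusted false-positive rate by Fisher's z, with d = atanh(r1 × r2) × √(112 − 3) and √109 = 10.44: rate = 1 − Φ(1.96 − d) + Φ(−1.96 − d).
- Residual standardised slope after adjusting for readiness: −r1 × r2 × (1 − rel) / (1 − rel × r1²).

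Worked example at 0.4/0.3: r1 × r2 = 0.12; d = 0.1206 × 10.44 = 1.26; rate = 1 − Φ(0.70) + Φ(−3.22), about 24%. With rel = 0.7 the residual slope is −0.12 × 0.3 / (1 − 0.7 × 0.16) = −0.036 / 0.888 = −0.041.

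| r1 / r2 | Spurious correlation | Unadjusted, Fisher | Unadjusted, simulated | Residual slope, rel 0.7 | Adjusted, rel 0.7 | Adjusted, rel 0.5 |
|---|---|---|---|---|---|---|
| 0.2 / 0.2 | −0.04 | 7% | 7% | −0.012 | 5% | 5% |
| 0.3 / 0.3 | −0.09 | 16% | 15% | −0.029 | 6% | 8% |
| 0.4 / 0.3 | −0.12 | 24% | 25% | −0.041 | 7% | 11% |
| 0.5 / 0.4 | −0.20 | 56% | 57% | −0.073 | 11% | 22% |

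The two unadjusted columns agree to within about one percentage point. The adjusted rates are from simulation. With error-free readiness (rel = 1), every row returns to about 5%.

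**In BMI z units.** No SD of change is stated. The planned 84% power for 0.16 implies:

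- 0.16 / [√(2/112) × (1.96 + 0.99)], about 0.41, with no design effect;
- about 0.36 with design effect 1 + 27 × 0.01 = 1.27;
- about 0.30 with that design effect and a t test on 6 degrees of freedom.

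The 0.3/0.3 and 0.5/0.4 rows then give, per SD of attendance, a spurious slope of −0.09 × 0.30 = −0.027 to −0.20 × 0.41 = −0.082. That is about 17% to 51% of the 0.16 target. At 0.2/0.2 it is −0.012 to −0.016, or 8% to 10%.

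**The case against.** The strongest reply is that the plan claims nothing causal here. Attendance is listed as a process measure, the sentences speak of relationships and association, no hypothesis concerns dose, and the main analysis counts students who complete only some sessions. This stands, and it is why the point is minor. A reader might infer that the trial's conclusion, or the decision on dissemination, rests on the attendance result. The documents do not support that. The longer programme is justified by consensus on long-term intervention and by pilot outcomes, and Aim 3 draws dissemination guidance from participant feedback.

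Second, part of the remedy may already be planned. The multilevel framework arguably covers school, and the baseline-covariate rule might be read to include baseline BMI z. The text is ambiguous on both. Readiness is absent on either reading.

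Third, the size depends on assumed correlations. This also stands: at 0.2/0.2 the rate is about 7%, and at 0.1/0.2 about 5%, which is essentially nominal. A reader might also infer that adding readiness cures the problem. That holds only if readiness is the sole common cause and is measured without error. Other causes of attendance, early weight change that affects later attendance, and school leavers with both fewer sessions and missing outcomes would all remain.

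Finally, a reader might want a per-session effect estimated with allocated arm as the instrument and comparison schools at zero sessions. The design does not support this. All intervention-school students receive annual motivational-interviewing discussions of BMI, eating and activity, and comparison students do not. ACTION also brings a caregiver newsletter and caregiver telephone calls. The calls follow clinic visits, but the discussions and newsletter do not depend on session count. Allocation can therefore act outside the sessions, and such an estimate would credit those effects to them.

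**Conclusion.** The point holds as a minor improvement to a secondary analysis. The stated adjustment is demographic only in one sentence and absent in the other, while a relevant baseline measure appears to be available and unused. Under no true session effect, the illustrative false-positive rate runs from about 7% to 57% over the assumed correlations shown, and weaker correlations leave it near 5%. Adjustment for readiness at an assumed reliability of 0.7 brings it to about 5% to 11%. The true size cannot be found from the documents. The conclusion rests on reading the waves as including a baseline readiness score and on 112 students in the arm. No randomised contrast, hypothesis test or sample size is affected.

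**What to change.** In section V.iii, Analysis of intervention effects:

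- Specify that both attendance analyses adjust for baseline readiness-to-change score, baseline BMI z score and the listed demographics, within the multilevel framework for school.
- Use the baseline readiness score only, because year 1 and year 2 values may themselves be changed by the sessions.
- State that the result is a non-causal association within the intervention arm and is not evidence of a per-session effect. Because adjustment leaves residual confounding, this label is needed as well as the covariates.
- Do not add an estimate with allocated arm as the instrument.
- Confirm in the assessment schedule that readiness is collected at baseline.

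The cost is a few lines of wording and two further covariates from data already planned for collection. Students without a baseline readiness score would need to be handled under the plan's missing-data approach.

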**Sample size and power analysis:** Given that incidence of overweight/obesity after 2 years (percent of students who were not overweight or obese at baseline but who become overweight or obese) is the primary outcome for the prevention intervention (discussing BMI results/healthful eating/physical activity with students using MI) (**Hypothesis 1a**), calculations are based on the ability to detect a 7.4% incidence difference between the intervention and comparison schools as previously reported from a policy-based school intervention to prevent overweight and obesity. Recruitment of 120 students per school with ~36% who will be overweight or obese and ~64% who will not be overweight or obese (estimated from our previous experience) will give us a total sample of 960 students. Student retention rates in the proposed schools from 9th – 11th grades and from 10th – 12th grades range from 52% to 92% (mean of 72%). In our previous R21, 5% dropped out of the study and 8% left school. Taking into account the schools' retention rates and also our small dropout rate from our previous NIH-funded R21, we are using 35% as the potential attrition rate to calculate a sufficient sample size for testing: 1) BMI result/healthful eating/physical activity discussion with MI component, and also for 2) the weight management component. ~77 students per school are anticipated to be <85th percentile (120 students × 64% who are <85th percentile). If there is 35% attrition, ~50 students per school (400 total) will be available to calculate incidence of overweight/obesity. Based on analysis of our NIH-funded R21 study at two high schools, we used a value of 0.01 for the intraclass correlation (ICC). Therefore, with two-tailed alpha of 0.05 and power level of 0.80, differences of 6% to 10% will be detectable if incidence from the comparison schools range from 7% to 15%, respectively.

Due to higher than anticipated attrition at the high schools from baseline to 1st annual measurements, we will increase our current total sample enrollment (n=960) by 5%, to give a new total sample of 1008 participants.

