Analysis Plan: As a preliminary step, we will examine the skewness and kurtosis of all variables to assure no problematic deviations from normality. In the event of such deviations, we will use appropriate transformations or use non-parametric methods. Analyses will be conducted using SAS Version 9.3, STATA Version 12 and Mplus Version 5. All programs include capabilities to test models with categorical outcomes, missing data, and to account for a design that uses a multilevel or clustered framework.

- Pretest equivalence: To explore the possible size and direction of bias that may exist, the pretest equivalence of conditions across demographics, BMI percentile, and other outcome variables of interest will be assessed via t-tests on continuous items and  $\chi^2$  tests of categorical items from the pretest. Wilcoxon rank sum tests or appropriate transformations will be used for non-normal data. We will use the Bonferroni approach to correct for alpha inflation with an experiment-wise alpha of 0.05. For variables where there are significant differences, the baseline values will be included as covariates in the analysis of intervention effects.

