
analysis procedures to estimate outcomes for the school population.

Baseline values will be included as covariates in the mixed effects linear regression models for continuous dependent variables and the generalized estimating equation models for binary dependent values including the incidence of overweight or obesity or the presence or absence of specific components of the metabolic syndrome. For students who repeat grades, we will include "repeated grade" as a covariate. Intervention (coded 0=control and 1=intervention) will be entered as a fixed effect into the multilevel models predicting outcomes. One equation will be estimated for each of the outcomes of interest. This approach is conceptually identical to an analysis of variance or covariance (ANOVA or ANCOVA) but has two distinct advantages. First, it allows for the analysis of clustered data, and second, it avoids list-wise deletion of subjects with missing assessments. The model relaxes the restrictive assumption that the data are missing completely at random and provides unbiased estimates under the less restrictive assumption of missing at random. This approach to missing data, i.e., the use of techniques that include full information maximum likelihood estimation of missing values, will be used.

• **Analysis of semi-structured Interviews (Aim 3):** Parent and student interviews conducted following the intervention will be analyzed using standard qualitative assessment methods. [name] will lead this analytic process. The interviews will each be transcribed and distributed to the research team. Each member will review transcripts independently, identifying themes related to the stem questions as well as other emergent areas of interest. The analysis will proceed in an iterative fashion, with the team reviewing sets of 3 to 4 transcripts in each category (parent and student). Following the independent reading, the team will meet to list the full range of themes, identify anomalous or unanticipated findings, and revise the interview guides accordingly. This process will continue until the team has reached consensus. At that stage, the thematic list will be converted into a template for coding purposes. Interviews will be coded in NVivo 9 (Melbourne, Australia), a qualitative data analysis software package, at which point queries to refine analytic and interpretive understandings will be conducted.

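### The Hypothesis 1a incidence model adjusts for unnamed baseline values that are constant for that outcome; baseline BMI z score should be named as a fixed covariate

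*Combined protocol and SAP*

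**What the plan says.** Section V.iii, Sample size and power analysis, makes two-year incidence of overweight/obesity the primary outcome of the prevention component, and sizes the trial to "detect a 7.4% incidence difference between the intervention and comparison schools". Analysis of intervention effects defines the outcome as "Incidence of overweight and obesity after 2 years among students who were not overweight or obese at baseline".

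These statements bear on the covariates in that model:

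- **Analysis of intervention effects.** "Baseline values will be included as covariates in the mixed effects linear regression models for continuous dependent variables and the generalized estimating equation models", continuing "for binary dependent values including the incidence of overweight or obesity". The variable is not named. The only covariate this text names outright is whether a student repeated a grade. It likens the approach to ANOVA or ANCOVA.
- **The same text.** "One equation will be estimated for each of the outcomes of interest".
- **Pretest equivalence.** "the pretest equivalence of conditions across demographics, BMI percentile, and other outcome variables of interest will be assessed via t-tests on continuous items", with a Bonferroni correction at an experiment-wise 0.05. Then: "For variables where there are significant differences, the baseline values will be included as covariates in the analysis of intervention effects".

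Section V.i, Data Collection Measurements, has BMI percentile and BMI z score calculated from each participant's height, weight, sex and age.

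**The concern.** For BMI z score, HOMA-IR and the other continuous outcomes, the baseline value of the outcome is an obvious and useful covariate. For Hypothesis 1a it is not, because the cohort is defined by not having the outcome at baseline. The variable is a column of zeros and cannot be estimated apart from the intercept.

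A student's distance below the 85th percentile at entry should strongly predict who crosses it within two years, so this is the covariate one would want in the primary prevention model. The plan does not name it for that model. Its only stated way in is a significance test of baseline imbalance, which responds to chance differences between arms and not to how strongly the variable predicts the outcome.

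Two things are at stake. One is precision. The other is a fixed primary model: two analysts following the text could fit different Hypothesis 1a models, one with a baseline BMI term and one without.

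**Working it through.** **1. The plan's own figure.** Inputs from Sample size and power analysis: 8 schools, 50 analysable students each (200 per arm), ICC 0.01, two-sided 0.05, power 0.80. Design effect = 1 + 49 × 0.01 = 1.49; effective n = 200/1.49 = 134.2 per arm. An arcsine comparison of two proportions gives detectable reductions of 6.1 points from 7% and 9.9 points from 15%. This reproduces the stated 6% to 10%. No covariate enters the calculation, so this point leaves it unchanged.

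**2. The outcome's own baseline value.** Cohort: not overweight or obese at baseline. Outcome: overweight or obese at two years. Baseline status is therefore 0 for every student, has zero variance, and adjusts for nothing.

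**3. How often the pretest rule would admit BMI percentile.** The documents do not give the number of tests T, the cohort tested, or an ICC for baseline BMI. Assume T from 11 (five demographic items, BMI percentile, five Hypothesis 1b outcomes) to 30 (adding the remaining outcomes and scales). Under randomisation P = 2 × [1 − Φ(z/√DEFF)], with z = Φ⁻¹(1 − 0.025/T), which is 2.838 for T = 11 and 3.144 for T = 30. The plan's t-tests carry no stated allowance for clustering, so DEFF = 1 + (m − 1) × ICC inflates the rate.

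| Cohort tested | No clustering effect | ICC 0.01 | ICC 0.02 (assumed) |
|---|---|---|---|
| below 85th percentile, m = 77 | 0.2–0.5% | 1.8–3.2% | 4.8–7.4% |
| all recruits, m = 120 | 0.2–0.5% | 3.4–5.5% | 8.7–12.3% |

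The range is wide, but in every case the rule usually leaves BMI out.

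**4. What baseline BMI z could explain.** The documents give no association between baseline BMI and incidence, so this step rests on assumptions. Take a normal BMI z with 36% at or above the cut-off (the plan's proportion), keep the part below it, assume a two-year correlation r, and set the follow-up cut so that incidence is 7%, 10% or 15%. R² is the share of outcome variance explained. The fall in the risk-difference standard error (SE) under no effect is 1 − √(1 − R²) if school-level variance shrinks in proportion, or 1 − √[(0.99(1 − R²) + 0.50)/1.49] if only the student part shrinks.

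| r | R² at 7 / 10 / 15% | SE fall, proportional | SE fall, student part only |
|---|---|---|---|
| 0.5 | 2.6 / 3.3 / 4.3% | 1.3–2.2% | 0.9–1.4% |
| 0.6 | 3.8 / 4.9 / 6.5% | 1.9–3.3% | 1.3–2.2% |
| 0.7 | 5.6 / 7.2 / 9.5% | 2.8–4.9% | 1.9–3.2% |
| 0.8 | 8.4 / 10.9 / 14.3% | 4.3–7.5% | 2.8–4.9% |
| 0.9 | 14.1 / 18.1 / 23.8% | 7.3–12.7% | 4.8–8.2% |

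For scale, the plan's 5% enrolment increase (48 students) takes analysable students from 50 to 52.5 per school and lowers the SE by 1 − √[(0.99/52.5 + 0.01)/(0.99/50 + 0.01)] = 1.6%.

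**5. The logit scale behaves differently.** Under no effect the SE of the conditional log odds ratio is multiplied by 1/√(1 − R²), that is by 1.013 (r = 0.5, 7%) to 1.145 (r = 0.9, 15%). It rises. The conditional effect also moves away from zero. At 15% versus 7.6% (the 7.4-point target), with 200 per arm and the design effect held at 1.49, the unadjusted log odds ratio is −0.76, SE 0.406, |z| = 1.88. The adjusted values run from −0.79, SE 0.413, |z| = 1.92 (r = 0.5) to −0.95, SE 0.453, |z| = 2.10 (r = 0.9). Power can improve even though this SE does not fall. The upper value depends on holding the design effect fixed.

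**The case against.** The strongest reply is that a covariate equal to 0 for everyone cannot have been intended. The plan expressly lists incidence among the models that receive baseline values, the pretest paragraph uses the same term for variables that include BMI percentile, and BMI measures are calculated for participants. The reading that gives the sentence effect is some baseline BMI measure. This largely stands as an account of intent. A reader might infer that the plan commits to a Hypothesis 1a model without baseline BMI; the documents do not support that. They leave open whether BMI enters and, if so, as z score, percentile or raw BMI.

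A reader might also infer that the one-equation sentence rules out any second model. It says only that outcomes are modelled separately, and does not bar sensitivity analyses.

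The precision gain is assumed, not documented. At correlations of 0.5 to 0.6 it is only about 1% to 3%. The 13% end pairs r = 0.9 with 15% incidence, which in this model needs BMI z to drift upward (follow-up cut 0.23 against baseline cut 0.36). That also stands.

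Nor is the covariate certainly free. With 8 schools, a small-sample GEE convention of clusters minus parameters would move 6 degrees of freedom to 5 and the critical value from 2.447 to 2.571, about 5% larger. Other conventions keep 6, and the plan states none.

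**Conclusion.** The point holds as a specification gap in the primary prevention analysis, worth closing but not a threat to validity. The text names no usable baseline variable for the Hypothesis 1a model, and the one rule that mentions a BMI measure selects on chance imbalance and would usually not trigger.

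A reader might go further and conclude that the result would be biased or the trial underpowered. The documents do not support either: schools are randomised, so omitting the covariate leaves the estimate unbiased over randomisations, and the stated detectable differences use no covariate. The gap is also specific to this outcome, since the continuous outcomes have a baseline value that can be used.

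The documents cannot give the size of the loss. Under the assumed correlations (0.5 to 0.9) and incidence (7% to 15%), naming the covariate lowers the risk-difference SE by about 1% to 13% under no effect. The firmer benefit is that the primary model is fixed before results are seen.

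**What to change.** In Section V.iii, Analysis of intervention effects, name continuous baseline BMI z score as a fixed covariate in the Hypothesis 1a incidence model, regardless of observed balance. In Pretest equivalence, make the comparison descriptive and stop using its significance to choose covariates. If demographic covariates are wanted, list them in advance so that they do not lose their route into the model. Reporting a standardised risk difference alongside the model estimate is optional; it would match the scale of the 7.4-point planning target, but the plan names no effect scale and this is a preference.

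The cost is two or three lines of wording and no new data, because BMI z score is already calculated. Under some small-sample GEE conventions it may also cost one degree of freedom, so the convention should be stated at the same time.
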